### **Intensity and Causality Assessments**

Where appropriate, the investigator must assess the intensity (severity) of the AE based on medical judgment with consideration of any subjective symptom(s), as defined below:

#### ***Intensity (Severity)***

Mild            An AE is mild if the subject is aware of but can easily tolerate the sign or symptom.

Moderate      An AE is moderate if the sign or symptom results in discomfort significant enough to cause interference with the subject's usual activities.

Severe          An AE is severe if the sign or symptom is incapacitating and results in the subject's inability to work or engage in their usual activities.

For every AE in the study, the Investigator must assess the causality (Related or Not Related to the medical device or study procedure). An assessment of causality will also be performed by Study Sponsor utilizing the same definitions, as shown below:

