## 1 GLOSSARY OF TERMS

Names of Test Product(s)	Throughout this document, test product(s) will be referred to as the UNITY Vitreoretinal Cataract System (VCS).
Name of Comparator Product(s)	N/A
Adverse Device Effect (ADE)	
Adverse event related to the use of an investigational medical device or comparator.
 
Note: This definition includes adverse events resulting from insufficient or inadequate instructions for use, deployment, implantation, installation, or operation; any malfunction; and use error or intentional misuse.

Adverse Event (AE)	
Untoward medical occurrence, unintended disease or injury, or untoward clinical signs (including abnormal laboratory findings) in subjects, users or other persons, whether or not related to the investigational medical device or comparator and whether anticipated or unanticipated.
 
Note: For subjects, this definition includes events related to the investigational medical device, comparator, or the procedures involved. For users or other persons, this definition is restricted to the use of the investigational medical device or comparator.
 
Requirements for reporting Adverse Events in the study can be found in Section 11.

Anticipated Serious Adverse Device Effect (ASADE)	An effect which by its nature, incidence, severity, or outcome has been identified in the risk assessment.

Clinical Investigation Plan (CIP)	
The document(s) stating the rationale, objectives, design, and prespecified analysis, methodology, organization, monitoring, conduct, and record-keeping of the clinical investigation.
 
Note: The protocol and other documents referenced in the protocol (for example, the Statistical Analysis Plan, the Manual of Procedures, the Deviations and Evaluability Plan, and the Protocol Monitoring Plan) comprise the CIP.

Clinical Investigation Report (CIR) / Clinical Study Report	
The document describing the design, execution, statistical analysis, and results of a clinical investigation. The Clinical Investigation Report is synonymous with the Clinical Study Report.

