### 6.4 Safety Objective(s)

**Table 6–3 Safety Objective(s)**

[figure not shown]
Objective(s)	Endpoint(s)
To obtain device-specific safety clinical data	Adverse events (ocular and nonocular; serious and nonserious) Device deficiencies Secondary surgical interventions Unplanned intraoperative surgical procedures

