## 11 ADVERSE EVENTS AND DEVICE DEFICIENCIES

### 11.1 General Information

An AE is any untoward medical occurrence, unintended disease or injury, or untoward clinical signs (including abnormal laboratory findings) in subjects, users, or other persons, whether or not related to the investigational medical device (test product). Refer to the Glossary of Terms and figures below for categories of AEs and SAEs.

**Figure 11-1** Categorization of All Adverse Events

\*In this study, only AEs related to the investigational product/device (i.e., UNITY VCS) are considered as device related ADE.

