### ***Serious Adverse Events***

- Postoperative corneal incision site wound leakage
- Hypopyon
- Hyphema
- Toxic anterior segment syndrome
- Posterior capsular tear
- Vitreous prolapse
- Iridodialysis
- Posterior lens dislocation
- Chronic corneal edema (corneal stromal or epithelial swelling resulting in BCDVA of  $\leq 20/40$  at  $\geq 1$  month)
- Clinically significant cystoid macular edema
- Uncontrolled increase in IOP  $\geq 10$  mmHg over baseline and at least 25 mmHg
- Endophthalmitis
- Retinal detachment
- Pupillary block
- Suprachoroidal hemorrhage
- Vitreous hemorrhage
- Vision-threatening surgical problems
- Secondary surgical intervention (excluding posterior capsulotomy)

[figure not shown]
NOTE: Wound burps during the first week postoperatively, suture removal, planned blepharoplasty, and Nd:YAG capsulotomy (for PCO) are not considered adverse events for this study.

Any other potentially sight-threatening event may also be considered serious based on the judgment of the investigator and should be reported appropriately as delineated in Section [11.3](#).

AEs occurring in association with a device that is used in conjunction with the UNITY VCS (e.g., femtosecond laser) will be classified separately from those associated with the investigational device itself.

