### 11.3 Procedures for Recording and Reporting

AEs are collected from the time of informed consent. Any pre-existing medical conditions or signs/symptoms present in a subject prior to the start of the study (i.e., before informed consent is signed) are not considered AEs in the study and should be recorded in the Medical History section of the eCRF.

In addition, aqueous cells and flare, corneal edema, eye redness, raised IOP, subconjunctival hemorrhage, and superficial punctate keratitis are examples of early postoperative findings that are typically observed following ocular surgery. These are not considered AEs if they can be reasonably expected to resolve within 2 weeks and not result in any untoward long term visual outcome impact. Expected complications from use of femtosecond laser-assisted procedures as noted in Section 5.3 will not be considered device related AEs..

For each recorded event, the ADEs and SAEs documentation must include: date of occurrence, severity, treatment (if applicable), outcome, and assessments of the seriousness and causality. In addition, the investigator must document all device deficiencies reported or observed with the test product on the Device Deficiency eCRF. The site must submit all available information on ADEs, SAEs, and device deficiencies to the Study Sponsor immediately as follows:

- ADEs or SAEs are documented on the *Serious Adverse Event and Adverse Device Effect* eCRF within 24 hours of the investigator's or site's awareness.
- Device deficiencies are documented on the *Device Deficiency* eCRF within 24 hours of the investigator's or site's awareness.
- Additional relevant information after initial reporting must be entered into the eCRF as soon as the data become available.
- Document any changes to concomitant medications on the appropriate eCRFs.
- Document all relevant information from Discharge Summary, Autopsy Report, Certificate of Death etc., if applicable, in the narrative section of the *Serious Adverse Event and Adverse Device Effect* eCRF.

*Note:* Should the EDC system become nonoperational, the site must complete the appropriate paper *Serious Adverse Event and Adverse Device Effect* and/or *Device Deficiency* Form. The completed form is emailed to the Study Sponsor at [[contact]](mailto:[contact]) for USA-based sites and at [[contact]](mailto:[contact]) for AUS-based sites, according to the

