#### ***Causality***

Related	An AE classified as related may be either definitely related or possibly related where a direct cause and effect relationship with the medical device or study procedure has not been demonstrated, but there is a reasonable possibility that the AE was caused by the medical device or study procedure.
Not Related	An AE classified as not related may either be definitely unrelated or simply unlikely to be related (i.e., there are other more likely causes for the AE).

The Study Sponsor will assess the AEs and may upgrade the investigator's assessment of seriousness and/or causality. The Study Sponsor will notify the investigator of any AEs that are upgraded from nonserious to serious or from unrelated to related.

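### The stated adverse event causality rating joins device and procedure and is not reconciled with the device-only ADE rule, and the SAP specifies no ADE/SADE summary

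*Protocol*

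**What the plan says.** **Causality rating.** Protocol Section 11.3 requires a causality judgement for every AE: "Related or Not Related to the medical device or study procedure". The definition of Related uses the same joined wording and is met when "there is a reasonable possibility that the AE was caused by the medical device or study procedure". The sponsor makes its own assessment with the same definitions and may upgrade an event from unrelated to related.

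**Device-only classification.** The glossary defines an ADE as "Adverse event related to the use of an investigational medical device or comparator". The note to Figure 11-1 in Section 11.1 applies this to the study: "In this study, only AEs related to the investigational product/device (i.e., UNITY VCS) are considered as device related ADE". For other devices used in the same surgery, Section 11.1 says that associated events "will be classified separately from those associated with the investigational device itself". Section 11.3 adds: "Expected complications from use of femtosecond laser-assisted procedures as noted in Section 5.3 will not be considered device related AEs".

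**Objective and analysis.** The safety objective in Table 6–3 is "To obtain device-specific safety clinical data". SAP 5.3.1 plans counts, percentages and listings of adverse events. It specifies no table of ADEs or SADEs and no breakdown by relatedness.

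**The concern.** Two parts of Section 11 ask for different things. The rating in Section 11.3 accepts either source as grounds for Related. The ADE rule in Section 11.1 accepts only one of them. An investigator who applies the rating as worded has not recorded what the ADE rule needs, and neither section says how to get from one to the other.

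The design makes individual attribution important. Under Section 9.3 all eligible, consented subjects have cataract surgery with UNITY VCS, and under Section 7.4 there is no comparator. Device and procedure exposure therefore coincide, and no between-group contrast can separate their effects. Section 5.3 also says that the complications it describes are already known from phacoemulsification with an anterior segment system, so some events due to surgery alone can be expected among the serious ones.

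At stake is whether the report can give ADE and SADE counts by a prespecified rule. Those counts are the natural expression of a device-specific safety objective, and Section 7.2 intends the safety results to be compared with existing evidence.

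**Working it through.** The documents give no ADE rate, threshold or precision, so there is no plan figure to reproduce. The check is to trace typical events through the rules, then to show the size of the ambiguity with assumed counts.

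**Step 1: one scale or two?** The word *or* in the rating could mean that relatedness to each source is judged separately. The surrounding text leans towards a single scale. It speaks of causality in the singular, gives one definition per level, and describes sponsor upgrades as a move from unrelated to related. No criterion is given for telling device from procedure.

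**Step 2: trace four events, taking the rating as a single scale.**

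| Event and judged cause | Rating (11.3) | ADE (11.1)? | On the shared SAE/ADE eCRF? |
|---|---|---|---|
| Serious (e.g. posterior capsular tear), surgery alone | Related | No | Yes, as an SAE |
| Same serious event, UNITY VCS | Related | Yes, a SADE | Yes, as an SAE and ADE |
| Nonserious, surgery alone | Related | No | No |
| Nonserious, UNITY VCS | Related | Yes | Yes, as an ADE |

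For nonserious events, routing does the work: only an ADE belongs on that form. For serious events it does not. The first two rows have the same seriousness, the same causality code and the same form. Unless a further field exists, a SADE cannot be told from a procedure-only SAE by those entries.

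**Step 3: other devices.** Section 5.3 allows laser-assisted incisions and capsulotomies. A laser-related event could be rated Related as part of the procedure, yet Section 11.1 wants it kept apart from UNITY VCS events. The two-level rating has no place to record that.

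**Step 4: sponsor review.** On a single scale, an event already rated Related because of surgery has no higher level. A sponsor view that UNITY VCS also contributed would leave the rating unchanged.

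**Step 5: could device deficiency records substitute?** No. Section 11.1 says that not all ADEs or SADEs are due to a device deficiency.

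**Step 6: size, with assumed counts.** The only input from the documents is n = 100, the number of treated subjects targeted in Section 8. Let r be the number of eyes with a Related event and d the number with a device-related event. If only the joint code existed, 0 ≤ d ≤ r. Exact (Clopper-Pearson) limits for d of n are the 0.025 quantile of Beta(d, n − d + 1) and the 0.975 quantile of Beta(d + 1, n − d), with a lower limit of 0 when d = 0.

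- Assumed r = 10: d/n runs from 0/100 = 0% (95% CI 0 to 3.6%) to 10/100 = 10% (4.9 to 17.6%).
- Assumed r = 5: d/n runs from 0% (0 to 3.6%) to 5/100 = 5% (1.6 to 11.3%).

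The values of r are invented. The ranges apply only if no separate device attribution is recorded.

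**The case against.** A reader might infer that device effects cannot be separated from ordinary surgical complications in this trial, or that ADE and SADE counts cannot be derived. The documents do not support that, for these reasons:

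- Section 11 has to be read as a whole. The glossary, the Figure 11-1 note, the rule on other devices and the exclusion of expected laser complications all require device-level attribution. Section 11.4 asks for return of products associated with product-related AEs, which presupposes it too.
- A nonserious event reaches the SAE/ADE eCRF only if someone has judged it to be an ADE.
- The content of Figure 11-1, the eCRF and the MOP was not available. Any of them may already hold separate device and procedure items.
- Much routine surgical background is never recorded as an AE. Section 11.3 excludes typical early postoperative findings that can reasonably be expected to resolve within 2 weeks without long-term visual impact. Section 11.1 excludes first-week wound burps, suture removal and Nd:YAG capsulotomy for posterior capsule opacification.
- The study is descriptive, with no safety hypothesis, and SAP 5.3.1 lists every adverse event with further details.

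These points stand, and they limit the finding. They show that the protocol wants a device-specific classification. They do not show how its stated causality rating supplies one, and the exclusions do not cover the serious events listed in Section 11.1. The SAP gap remains however the rating is read.

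**Conclusion.** The point holds in a limited form. The rating stated in Section 11.3 does not by itself yield the ADE/SADE classification that Section 11.1 requires, chiefly for serious events and for events involving another device. SAP 5.3.1 specifies no ADE/SADE summary although the objective is device-specific.

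The first part rests on reading the rating as a single scale, which the wording favours but does not settle, and on there being no separate field in material that was not available. If such a field exists, the protocol needs only aligned wording. The SAP part depends on neither assumption.

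No stated figure in the plan is wrong. The 0 to 10 range in 100 eyes is an assumed illustration and not an estimate. This is an inexpensive improvement, best made before data are collected, because attribution added afterwards would be retrospective.

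**What to change.** **Protocol Section 11.3.** For every AE, require three separate Related / Not Related items: (1) UNITY VCS, (2) the surgical procedure, (3) any other device used, such as a femtosecond laser. Procedure and other device should not share an item, because Section 11.1 wants other-device events classified separately. Use the same items for the investigator and sponsor assessments, and let sponsor upgrades apply to each item. State that ADE status, and SADE status for serious events, follows item (1).

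**SAP 5.3.1.** Add counts and percentages of eyes with ADEs and with SADEs on the safety analysis set, shown separately from events related only to the procedure or to another device.

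**Cost.** One or two extra eCRF items, or none if they are already captured, plus one extra table and a few lines of text. Sample size and visits are unchanged.

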#### ***Causality***

Related	An AE classified as related may be either definitely related or possibly related where a direct cause and effect relationship with the medical device or study procedure has not been demonstrated, but there is a reasonable possibility that the AE was caused by the medical device or study procedure.
Not Related	An AE classified as not related may either be definitely unrelated or simply unlikely to be related (i.e., there are other more likely causes for the AE).

The Study Sponsor will assess the AEs and may upgrade the investigator's assessment of seriousness and/or causality. The Study Sponsor will notify the investigator of any AEs that are upgraded from nonserious to serious or from unrelated to related.

## **11.4 Return Product Analysis**

Study Sponsor representatives and their contact information are provided in the MOP that accompanies this protocol.

Alcon study products associated with device deficiencies and/or product related AEs should be returned and must include the Complaint number which will be provided by Study Sponsor after the case is entered in the Study Sponsor's Global Product Complaint Management System (GPCMS).

## **11.5 Unmasking of the Study Treatment**

Not applicable; this study is open-label.

## **11.6 Follow-Up of Subjects with Adverse Events**

The investigator is responsible for adequate and safe medical care of subjects during the study and for ensuring that appropriate medical care and relevant follow-up procedures are maintained after the study.

The investigator should provide the Study Sponsor with any new safety information (which includes new AEs and changes to previously reported AEs) that may affect the safety evaluation of the device. For AEs that are unresolved/ongoing at time of discontinuation, any additional information received at follow-up should be documented in the eCRFs up to study completion (i.e., database lock). Any additional data received up to 6 months after a subject completed the study should be documented and available upon the Study Sponsor's request.

All complaints received after this time period will be considered and processed as spontaneous (following the postmarket vigilance procedures) and should be communicated to the medical device's manufacturer as per local requirements. The investigator should also report complaints on non-Alcon products directly to the manufacturer as per the manufacturer's instructions or local regulatory requirements.

## **11.7 Pregnancy in the Clinical Study**

Pregnancy is not reportable as an AE; however, complications may be reportable and will be decided on a case-by-case basis. An Alcon form will be utilized to capture all pregnancy-related information until birth of the child.

# **12 ANALYSIS PLAN**

## **12.1 Subject Evaluability**

Final subject evaluability must be determined prior to locking the database, based upon the Deviations and Evaluability Plan.

## **12.2 Analysis Sets**

All eligible subjects will be screened to determine if they meet all inclusion and no exclusion criteria. Subjects who provide informed consent will be considered enrolled in the study.

### **12.2.1 All-Implanted Analysis Set**

The primary analysis set for effectiveness outcomes will be the all-implanted analysis set. The all-implanted analysis set includes all eyes with successful completion of the cataract surgery, including IOL implantation.

### **12.2.2 Safety Analysis Set**

The safety analysis set will include all eyes with attempted use of the UNITY VCS (successful or aborted after contact with the eye) and will be used for the safety outcomes. Attempted use of the UNITY VCS is defined as any time the device makes contact with the eye.

## **12.3 Demographic and Baseline Characteristics**

Demographic and baseline characteristics will be summarized for each subject. Counts and percentages will be presented for categorical variables such as sex, age, race and ethnicity. Sample size (N), mean, standard deviation, median, minimum, and maximum will be presented for continuous variables such as age.

## 12.4 Effectiveness Analyses

### 12.4.1 Analysis of Primary Effectiveness Endpoint

The primary performance endpoint is the percent of ‘yes’ responses to the question: *Did UNITY VCS using anterior segment surgical functionality perform per the intended use as defined in Protocol Section 5.1?*

#### 12.4.1.1 Statistical Hypotheses

No hypothesis testing of the primary effectiveness endpoint is planned.

#### 12.4.1.2 Analysis Methods

Standard descriptive statistics will be presented for the primary effectiveness endpoint based on the type. For categorical summaries, statistics will include sample size, number in category, and percentage in each category. For continuous summaries, number of subjects, mean, median, standard deviation, minimum, maximum, and two-sided 95% confidence intervals for both mean and median will be reported. Individual subject data listings will also be provided.

### 12.4.2 Analysis of Secondary Effectiveness Endpoints

The secondary performance endpoint is time from incision entry to incision closure.

#### 12.4.2.1 Statistical Hypotheses

There are no hypothesis tests of the secondary effectiveness endpoints planned.

#### 12.4.2.2 Analysis Methods

The number of subjects, mean, median, standard deviation, minimum, maximum, and two-sided 95% confidence intervals for both mean and median will be reported for the secondary endpoint. Individual subject data listings will also be provided.

## 12.5 Handling of Missing Data

No imputation of missing data is planned.

## 12.6 Safety Analyses

The safety endpoints are:

- Adverse events (ocular and nonocular; serious and nonserious)

- Secondary surgical interventions
- Unplanned intraoperative surgical procedures
- Device deficiencies

## 12.6.1 Analysis of Safety Endpoints

The focus of the safety analysis will be a comprehensive descriptive assessment of the occurrence of adverse events as well as the other listed parameters above.

### 12.6.1.1 Statistical Hypotheses

There are no safety hypotheses planned in this study.

### 12.6.1.2 Analysis Methods

For all safety measures, descriptive statistics will be presented based on the type. For categorical variables, summary statistics will include sample size (subjects/eyes), number in category, and percentage in each category. For continuous variables, number of subjects/eyes, mean, median, standard deviation, minimum, and maximum will be reported. Individual subject data listings will also be provided.

## 12.7 Interim Analyses and Reporting

No interim analyses are planned.

## 12.8 Sample Size Justification

Based on a sample of 100 surgeries, the expected half-width of the 95 % confidence interval for the percentage of surgeons reporting 'yes' to the question "***Did UNITY VCS using anterior segment surgical functionality perform per the intended use as defined in Protocol Section 5.1?***" will be  $1.96 \cdot \sqrt{p(1-p)/100}$ . This half-width is widest at  $p = 50\%$ . Under this conservative assumption, the expected half-width is <10% given the sample size of 100.

Allow enrollment for an additional 10% for screen failure and 10% for lost to follow-up to ensure 100 completed subjects. (See also Section 8 of this protocol for more details.)

